## ABBREVIATIONS AND DEFINITIONS

ADE	Adverse Device Effect
AE	Adverse Effect
BCDVA	Best-Corrected Distance Visual Acuity
BP	Blood Pressure
BT	Body Temperature (Fahrenheit)
CDC	Center for Disease Control
CRA	Clinical Research Associate
CFR	Code of Federal Regulations
CRF	Case Report Form
CRC	Clinical Research Coordinator
Evolute®	Punctal Plug Delivery System
FDA	Food and Drug Administration
GCP	Good Clinical Practice
HIPAA	Health Insurance Portability and Accountability Act
ICF	Informed Consent Form
ICH	International Conference on Harmonisation
ICH E6	International Conference on Harmonisation Guidance for Industry Good Clinical Practice: Consolidated Guidance
IEC	Independent Ethics Committee
IOP	Intraocular Pressure
IRB	Investigational Review Board
ITT	Intent-to-treat
MedDRA	Medical Dictionary for Regulatory Activities
mmHg	Millimeters of Mercury
NCR	No Carbon Required
NDE	Non-drug eluting
NSR	Non-Significant Risk
PP	Per Protocol
QC	Quality Control
OH	Ocular Hypertension
OTC	Over-the-Counter
POAG	Primary Open-Angle Glaucoma
PPDS	Punctal Plug Delivery System
SADE	Serious Adverse Device Event
SAE	Serious Adverse Event
Study Subject	An individual that has signed a HIPAA and study consent form
Subject	Individual being considered for enrollment in to the study
UP	Unanticipated Problem
VA	Visual Acuity

[figure not shown]
## STUDY SYNOPSIS

### **STUDY PROTOCOL NUMBER:** TGLA-2021-01

**STUDY PROTOCOL TITLE:** A 90-Day, Open-Label, Multi-Site, Pilot Study Evaluating the Safety and Intraocular Lowering Effect of Delivering Travoprost using a Punctal Plug Delivery System (Evolute®) in Subjects with Elevated Intraocular Pressure

**SPONSOR:** Mati Therapeutics Inc.

**INVESTIGATIONAL PRODUCT, OPEN-LABEL:** The Travoprost Evolute (Travoprost Punctal Plug Delivery System) is an L-shaped, silicone punctal plug with a drug eluting core that contains travoprost (active). The Travoprost Evolute is pre-loaded onto a disposable inserter tip and individually packaged and sterilized to prevent contamination. The Travoprost Evolute is stored at refrigerated temperature.

**NUMBER OF SITES:** Up to 8 sites within the U.S.A.

**STUDY POPULATION:** Up to 30 qualified male or female subjects (~30 qualified eyes) who have given HIPAA and informed consent, have met all screening, washout and treatment phase inclusion/exclusion criteria of the study, will be enrolled and will receive a Travoprost Evolute inserted in to the lower punctum of each eye.

**STUDY OBJECTIVE:** Using a punctal plug delivery system (Evolute) to deliver a hypotensive (travoprost) drug to the eye, evaluate the safety and ocular effects of a Travoprost Evolute system in reducing intraocular pressure in individuals diagnosed with OAG or OH.

**STUDY DESIGN:** This is a pilot, open-label, multi-center clinical study. Each potential subject that has given HIPAA and informed consent and has meet all screening inclusion/exclusion criteria will undergo a six-week washout phase where they will discontinue the use of their topical hypotensive medication. In addition, during the washout phase, each potential study subject will also discontinue the use of all prohibited systemic medications.

After the six-week washout, each potential subject will return for a baseline visit (Visit 2). Investigators will verify that a potential subject has discontinued the use of their topical hypotensive medication(s) and all their prohibited systemic medications for the last 6 weeks. In addition, each subject will have discontinued the use of all other ocular drops, gels or ointments 24 hours prior to the visit (Visit 2) and continues to meet all screening and washout criteria. After completing the baseline examination, each potential subject that meet all baseline

inclusion/exclusion for the treatment phase of the study will have his/her lower puncta of each eye inserted with a Travoprost Evolute®. Each study subject will be instructed to return to the investigator's office the next day, seven, 28, 60 and 90 after the insertion of their plugs for follow-up examinations.

**SUBJECT SELECTION:** The following are inclusion and exclusion criteria for a prospective study subject

**i. Screening Phase**

a. **INCLUSION Criteria:** The following are requirements a subject must meet in order to be considered for inclusion into the screening phase of the study:

1. Male or female subject, 18 years of age or older at the time of the screening examination and has been diagnosed with bilateral OAG or OH
2. A subject must be able and willing to read, comprehend and give authorization for Use/Disclosure of Health Information (HIPAA) and informed consent
3. A subject must not have taken any ocular hypertension medication(s) within the last 12 hours of the screening visit unless in the opinion of the screening physician it poses an undue risk.
4. A subject must be willing to have the **lower puncta of each eye** inserted with a study plug
5. A subject's screening visit (pre-washout) IOPs, measured between 8:00 and 10:00 AM, is less than 22 mmHg in both eyes
6. A subject IOPs are currently controlled (< 22 mm Hg) with a topical prostaglandin or in conjunction with one other topical ocular hypotensive drug, not including any fixed-combination formulations (i.e., Cosopt, Combigan, Azarga, etc.), in both eyes for at least one month
7. A subject must be willing to comply with study instructions and agree to complete the entire course of the study
8. A subject must agree to make all office appointments and have all office visits occur between 8:00 and 10:00 AM
9. Women of child-bearing potential must not be pregnant or lactating, must have a negative pregnancy test at screening and must be practicing an adequate method of birth control, including intrauterine device (IUD); oral, dermal ("patch"), implant or injected contraceptives; tubal ligation; or barrier methods with spermicide
10. A subject has a Best-Corrected Distance (Glasses), pinhole visual acuity of 20/100 (Snellen) or better in both eyes
11. A subject has documented perimetry results within the last 6 months prior to the Screening Visit for both eyes

**NOTE:** If perimetry measurement are older than 6 months, perform automated perimetry at the screening visit

12. A subject has documented central corneal thickness measurements between >500 µm and <600 µm in both eyes

**NOTE:** if corneal thickness data is not available, measure corneal thickness of each eye using pachymetry at the screening visit

b. **EXCLUSION Criteria:** If any of the below criteria apply to a potential study subject, the subject does not qualify for enrollment into the screening phase of the study:

1. A subject with a history of non-response to topical prostaglandin eye drops for OAG/OH
2. A subject with angle-closure glaucoma, neovascular glaucoma, traumatic glaucoma or iridocorneal endothelium syndrome in either eye
3. A subject with a known sensitivity to travoprost, fluorescein, topical anesthetic, silicone, any inactive ingredient of the Travoprost Evolute® or any other products required for study procedures
4. A subject with  $\geq 0.9$  vertical cup or completely notched optic nerve head rim in either eye
5. A subject with any functionally significant visual field loss or progressive field loss within the last year in either eye
6. A subject with a history of complications, AEs, trauma or disease in the nasolacrimal area, whether or not it was due to punctal plug wear, including but not limited to dacryocystitis, inflammation or canaliculitis in either eye
7. A subject with a history of intolerance to punctal plugs or a known sensitivity to any inactive ingredient of the punctal plug, silicone, topical anesthetic, or any other products required for the study
8. A subject with structural lid abnormalities (i.e., ectropion, entropion) in either eye
9. A subject with an active lid disease in either eye (i.e., moderate or severe blepharitis, meibomianitis) that requires medical treatment
10. A subject with any clinically significant (moderate or severe) lid, conjunctival or corneal findings in either eye at the screening visit
11. A subject with a history of chronic/recurrent inflammatory eye disease (i.e., scleritis, uveitis, herpes keratitis) in either eye
12. A subject who would require the use of any ocular medication(s), an over-the-counter drop(s), ointment(s) or gel(s), other than the study hypotensive medication(s) in either eye during the study period
13. A subject who has had any ophthalmic surgical procedures (i.e., glaucoma laser, minimally invasive glaucoma surgery, cataract, refractive, etc.) in either eye within the last six months or will require ophthalmic surgery before completing the study
14. A subject with a history of penetrating keratoplasty in either eye
15. A subject requiring the use of a contact lens in either eye at any time during the study period
16. A subject with advanced diabetic retinopathy, branch retinal vein occlusion or central retinal vein occlusion in either eye
17. A subject with a history of macular edema in either eye
18. A subject currently on any systemic medication [i.e., beta-blocker, carbonic anhydrase inhibitors, corticosteroids (including dermal), etc.] that may have an effect on the subject's IOP, or who will require its use during the study period

**NOTE:** An inhaled steroid, systemic beta-blocker or  $\beta$ -adrenoceptor antagonist may be permitted, providing the subject has maintained a stable dosage regimen for at least the last three months

19. A subject with an uncontrolled systemic disease or a medical condition that may increase the risk associated with study participation or administration of study treatment or that may interfere with the interpretation of study results (e.g.,

autoimmune disease if the subject is on chronic medications and has ocular involvement; host-versus-graft disease)

20. A subject currently participating or has participated within the last 30 days prior to the start of this study in a drug, device or other investigational research study.

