## ii Washout Phase

After the screening phase (process), each subject meeting all screening inclusion/exclusion criteria must be willing to:

1. DISCONTINUE the use of his/her topical hypotensive medication(s) for the next six-weeks and not to use his/her hypotensive medication for the duration of the study
2. DISCONTINUE the use of all other ocular drops, gels or ointments that have not been prescribed by the investigator, 24 hours prior to Visit 2 and for the duration of the study
3. DISCONTINUE the use of all systemic medication that are PROHIBITED by the protocol for the duration of the study. Systemic medication(s) being used by a subject at the Screening visit and is permitted by the protocol, may continue the medication(s), however the **concentration and dosing frequency** must remain the same throughout the washout and treatment phases of the study.

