### 2.1 Background Information

Open-angle glaucoma (OAG) is a chronic ocular disorder characterized by elevated intraocular pressure (IOP) with clinical signs of visual field loss and/or optic nerve damage with patients rarely experience any ocular symptoms. If the condition is left untreated, irreversible vision loss due to optic nerve damage will occur. The effect of elevated IOP on the optic nerve is gradual, leading to vision loss that patients may not realize until they have irreversibly lost a majority of their vision.

Based on estimates from the World Health Organization and the Glaucoma Foundation, this chronic disease is believed to affect approximately 67 to 105 million people worldwide ([Leonard 2002](#)) and is the leading cause of irreversible blindness worldwide. In 2011, 2.71 million people in the United States had OAG, by 2050 it is estimated that 6.3 million people in the United States will have OAG.

Treatment however of OAG/OH by nature is a disease where compliance tends to be a significant problem due to the fact patients lack positive feedback from treatment. Treatment benefits with topical hypotensive medications are designed to prevent worsening rather than improving visual function by reducing IOP, which is not noticeable by patients.

[figure not shown]
Treatment compliance is therefore a key issue in the successful control of OAG/OH and the prevention of vision loss. Traditionally, the term compliance has been employed to mean the extent to which a patient remembers and complies with the physician's advice of when, and amount of medication to use. When treating a condition with an ocular drop from a bottle, treatment also depends upon the patients' physical ability to properly instill/place the correct amount of the medication/drop on the eye. A patients' ability to correctly self-administer ocular drops can be affected by a number of factors such as coordination, manual dexterity, n, good vision, all of which tend to decrease in aging glaucoma patients, and the presence of co-morbid conditions ([Choy et al. 2019](#)). Study has also shown that adding a second medication is associated with a statistically significant decrease in compliance ([Robin 2005](#)).

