### 5.2.1.1 Screening Phase - Inclusion Criteria

The following are requirements a subject must meet in order to be considered for inclusion into the study screening phases of the study:

1. Male or female subject, 18 years of age or older at the time of the screening examination and has been diagnosed with bilateral OAG or OH
2. A subject must be able and willing to read, comprehend and give Authorization for Use/Disclosure of Health Information (HIPAA) and informed consent
3. A subject must not have taken any ocular hypertension medication(s) within 12 hours of the screening visit
4. A subject must be willing to have the lower puncta of each eye inserted with a study plug
5. A subject's screening visit (pre-washout) IOPs, measured between 8:00 and 10:00 AM, is less than 22 mmHg in both eyes
6. A subject IOPs are currently controlled (< 22 mm Hg) with a topical prostaglandin or in conjunction with one other topical ocular hypotensive drug, not including any fixed-combination formulations (i.e., Cosopt, Combigan, Azarga, etc.), in both eyes for at least one month
7. A subject must be willing to comply with study instructions and agree to complete the entire course of the study
8. A subject must agree to make all office appointments and have all office visits occur between 8:00 and 10:00 AM
9. Women of child-bearing potential must not be pregnant or lactating, must have a negative pregnancy test at screening and must be practicing an adequate method of birth control, including intrauterine device (IUD); oral, dermal ("patch"), implant or injected contraceptives; tubal ligation; or barrier methods with spermicide
10. A subject has a Best-Corrected Distance (Glasses), pinhole visual acuity of 20/100 (Snellen) or better in both eyes
11. A subject has documented perimetry results within the last 6 months prior to the Screening Visit for both eyes

**NOTE:** If perimetry measurement are older than 6 months, perform automated perimetry at the screening visit

12. A subject has documented central corneal thickness measurements between >500 µm and <600 µm in both eyes

**NOTE:** if corneal thickness data is not available, measure corneal thickness of each eye using pachymetry at the screening visit

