### 5.2.2 Washout Phase - Criteria

After the screening phase (process), each subject meeting all screening inclusion/exclusion criteria must be willing to:

- 1) DISCONTINUE the use of his/her hypotensive medication for the next six-weeks (Note: If desired, an investigator can perform the six-week washout by placing the subject on monotherapy with a topical CAI for 5 weeks, then during the last week, discontinue the use of the topical CAI). Each subject will be instructed not to use his/her hypotensive medication for the duration of the study
- 2) DISCONTINUE the use of all other ocular drops, gels or ointments that have not been prescribed by the investigator, 24 hours prior to Visit 2 and for the duration of the study
- 3) DISCONTINUE all systemic medication that are PROHIBITED by the protocol for the duration of the study. Systemic medication(s) being used by a subject at the Screening visit and is permitted by the protocol, may continue the medication(s), however the **concentration and dosing** frequency should remain the same throughout the washout and treatment phase of the study

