### 7.4 Study Visit Phases/Schedule

#### 7.4.1 Visit 1 - Screening Phase (Qualification Visit)

At this visit, prior to any study specific procedure or examination, a subject must read, comprehend and give written Authorization for Use/Disclosure of Health Information (HIPAA) and Informed Consent to participate in the study. Once all forms have been signed, the investigator and/or his or her staff will perform the following screening assessments/examinations.

- a. Verify a subject has not used any hypotensive ocular drops within the last 12 hours of the screening visit
- b. A female subject of child-bearing potential will have a urine pregnancy test performed
- c. Record subject's demographic data and medical history for past 6 months
- d. Measure subject's temperature, heart rate and blood pressure
- e. Record subject's Best-Corrected (Glasses) Distance or Pinhole Visual Acuity
- f. Verify automated perimetry results have been measured and documented in the subject's chart within the last 6 months

**NOTE:** If perimetry measurement are older than 6 months, perform automated perimetry at the screening visit

g. Verify corneal thickness measurements are documented in the subject's chart

**NOTE:** If corneal thickness data is not available, measure corneal thickness of each eye using contact or non-contact pachymetry at the screening visit

h. Perform a slit-lamp examination of each eye

i. Perform a non-dilated fundus exam of each eye, including the evaluation of the lens

j. Record IOP measurement of each eye

k. Record concomitant medication use

If at any time during the screening examination it is determined a subject does not meet a screening inclusion/exclusion criterion, at that point any additional screening assessments-examinations will be discontinued.

After the screening procedures and examinations have been completed, each qualified subject that meets all study inclusion/exclusion criteria will be asked to enter the washout phase of the study and will be sequentially assigned an ID number ([Section 6.1](#)). In addition, the ID number and the study subject initials will be recorded on study case report forms, in lieu of recording his/her name, in order to maintain subject confidentiality.

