#### 7.4.2 Washout Phase (Six-week duration)

During the washout phase of the study, each subject will be instructed to discontinue the use of his/her topical hypotensive medication(s) for the next six-weeks. In addition, the subject will be instructed not to use any other ocular drops, gels or ointments 24 hours prior to the Baseline visit (Visit 2) in his/her eyes that have not been prescribed by the investigator.

Systemic or topical medications that are being used at the Screening Visit, that are considered necessary for the subject's welfare and are PERMITTED by the protocol ([Sections 5.2.1](#)), may continue to be used as long as the concentration and dosing frequency of the medication(s) will remain the same throughout the entire duration of the study.

Systemic medications that are PROHIBITED by the protocol, must be discontinued during the washout phase. All ocular drops, gels or ointments being used by the subject must be discontinued 24 hours prior to Visit 2. Should the subject qualify for the treatment phase of the study, they will be asked to continue for an additional  $90 \pm 7$  days not to use any systemic or topical medications during the treatment phase of the study.

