## 7.5 Unscheduled Visit

The investigator has the option of bringing a study subject back in for an unscheduled visit any time during the washout or treatment phase of the study for safety reasons (e.g., subject complaint of moderate or severe ocular symptoms, an AE). An unscheduled visit CRF should be completed. At minimum the investigator should record the following:

- a. Record any change in concomitant medication use
- b. Inspection of both punctal plugs via the slit-lamp
- c. Slit-Lamp examination, both eyes
- d. Measure IOP, both eyes
- e. Recording of any reported adverse events/adverse device events

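### The synopsis waives the 12 drop-free hours where they pose undue risk; sections 5.2.1.1 and 7.4.1 do not, and no criterion expressly keeps a waived patient out of the washout

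*Combined protocol and SAP*

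**What the plan says.** Synopsis, Screening Phase, inclusion criterion 3, rules out ocular hypertension medication "within the last 12 hours of the screening visit unless in the opinion of the screening physician it poses an undue risk". Section 5.2.1.1, item 3, states the rule without an exception: "A subject must not have taken any ocular hypertension medication(s) within 12 hours of the screening visit". The Visit 1 procedure in section 7.4.1, item a, is equally unconditional: "Verify a subject has not used any hypotensive ocular drops within the last 12 hours of the screening visit". So is item b of the study variables listed in the synopsis.

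Subjects who meet the screening criteria go into the washout. The synopsis requires them to be willing to "DISCONTINUE the use of his/her topical hypotensive medication(s) for the next six-weeks", and section 7.4.2 repeats that "each subject will be instructed to discontinue the use of his/her topical hypotensive medication(s) for the next six-weeks". Section 5.2.2 adds an option that the synopsis lacks. The investigator may choose a bridged version instead: "placing the subject on monotherapy with a topical CAI for 5 weeks, then during the last week, discontinue the use of the topical CAI".

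The schedule of assessments has no visit between Visit 1 and Visit 2. On extra visits, section 7.5 says: "The investigator has the option of bringing a study subject back in for an unscheduled visit any time during the washout or treatment phase". Its examples are symptom complaints and adverse events. Section 2.1 describes open-angle glaucoma as a condition "with patients rarely experience any ocular symptoms".

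**The concern.** The waiver and the washout work against each other. The waiver is for a patient whose physician thinks 12 hours without drops is too risky. Its effect is to let that patient pass screening into a much longer period without them. The washout criteria ask only whether the subject is willing to stop. They do not ask the physician to revisit the risk judgement.

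Two things are at stake. The first is subject protection: the exception can admit the people least suited to the washout. The second is entry status. A site that follows the synopsis enrols someone who, under section 5.2.1.1, did not meet the inclusion criteria. Section 5.4.2.2 lists that as improper entry and a ground for disqualification. Section 10.1 allows subjects with such violations to be left out of the primary analysis.

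**Working it through.** The plan gives no figure to reproduce on this point. The check is a comparison of texts plus one ratio.

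**Step 1. The four statements of the 12-hour rule.**

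| Place | 12 hours required | Exception for undue risk |
|---|---|---|
| Synopsis, screening inclusion 3 | yes | yes |
| Synopsis, study variable b | yes | no |
| Section 5.2.1.1, item 3 | yes | no |
| Section 7.4.1, item a | yes | no |

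The exception stands in one place against three, one of which is in the synopsis itself. No section of the available text says which version governs.

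**Step 2. Length of exposure.**

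- Waived interval: 12 hours.
- Default washout: 6 weeks × 7 days × 24 hours = 1,008 hours; 1,008 / 12 = 84.
- With the CAI bridge, only the last week is free of hypotensive drops: 1 × 7 × 24 = 168 hours; 168 / 12 = 14. The usual regimen is still stopped for all six weeks.
- Pressure readings scheduled between Visit 1 and Visit 2, 6 × 7 = 42 days: 0.

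The ratios compare durations. They do not measure risk.

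**Step 3. Does another provision close the gap?**

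- *Exclusion 12* concerns subjects who need ocular medication during the study, but it makes an exception for study hypotensive medication. It does not clearly reach a patient who cannot safely stop hypotensive drops.
- *Exclusion 19* covers uncontrolled systemic disease or a medical condition that raises the risk of participation. An investigator could use it here, but it is general and does not mention going without drops.
- *The CAI bridge* is optional, appears only in section 5.2.2, and still leaves one week without a hypotensive drop.
- *Unscheduled visits* (section 7.5) are optional, and a complaint is an unreliable prompt in a condition with few symptoms.
- *Rescue* (section 7.10.1) applies above 34 mmHg or on undue medical risk. The first limb needs a reading, and none is scheduled. The second uses nearly the same words as the waiver, so the judgement that let the patient in could also trigger rescue. Either way it acts after exposure has begun.
- *Withdrawal* by the investigator or Medical Monitor (section 5.4) is likewise a later remedy.

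None of these says what to do with a waived patient at the point of entering washout.

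**The case against.** The strongest reply is that this is a stray clause. Three of the four statements have no waiver, including the Visit 1 procedure that sites carry out. A site making that check would normally find the missing drop-free hours before washout starts. A physician who thought 12 hours unsafe would also have to pass over exclusion 19 to start a six-week washout, and on one reading exclusion 12 as well. Unscheduled visits with pressure measurement, rescue and withdrawal all remain available. Much of this stands. It makes the event unlikely, and it makes disqualification after plug insertion depend on successive lapses at the site. It does not remove an eligibility rule that exists in two versions, one of which expressly admits these patients.

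A reader might infer several stronger things that the documents do not support:

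- *That the waived patient goes without all drops for six weeks.* Section 5.2.2 permits a CAI for five of them. The documents also disagree on non-hypotensive drops: the washout criteria stop these 24 hours before Visit 2, while the schedule and section 7.9.1 stop them from screening.
- *That each such patient is one of the 30 subjects.* That cap applies to those who receive plugs. The waiver acts on screened candidates, whose number is not stated.
- *That a patient rescued during washout would be lost without replacement.* The no-replacement rule in section 5.4.3.1 describes a subject returning to have plugs removed, so it fits poorly where no plug was inserted.
- *That the waiver distorts the screening pressure.* The documents give no figure for such a shift.

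**Conclusion.** The point holds as a conflict between eligibility rules with a consequence for subject protection. On the synopsis wording, a patient judged at undue risk from 12 hours without drops may enter a washout with six weeks, or one week if bridged, without any hypotensive drop: 84 or 14 times the waived interval, with no scheduled pressure check before Visit 2. On the body text the same patient should not have been entered.

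This rests on two assumptions. The first is that the risk named in the waiver is the risk of withholding drops, which is the natural reading. The second is that no text outside the available sections ranks the synopsis against the body. The frequency is unknown but probably low, because exclusions 4 and 5 remove advanced or progressing disease and pressure must be controlled below 22 mmHg at entry. No effect on the primary estimate is claimed. The correction should be made because it protects patients and costs little.

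**What to change.** 1. In synopsis screening inclusion 3, delete everything from the word *unless* onward, so that it agrees with section 5.2.1.1, section 7.4.1(a) and study variable b.
2. Add to the screening exclusions in both the synopsis and section 5.2.1.2: *A subject for whom, in the investigator's opinion, stopping topical hypotensive medication for the washout poses an undue risk.*

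The deletion alone aligns the texts. The new exclusion is still needed, because it applies the physician's judgement to the washout itself, including for a patient who managed the 12 hours without drops. The cost is a wording amendment and the loss of a few candidates who could have entered under the waiver.
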